### 1.7 BioMimics 3D Study Purpose

The BioMimics 3D Study is designed to enable the collection, analysis, reporting and presentation of data from use of the BioMimics 3D Stent System purchased by the hospital or clinic and used in accordance with the Instructions for Use associated with the product's CE Mark approval. The intent of this post-market observational study is to increase the understanding of the performance of the BioMimics 3D Stent System in a larger population of patients representative of a real-world situation. In addition, a broader cohort of interventionalists (i.e., angiologists, cardiologists, radiologists and vascular surgeons) will be included than that so far involved in Veryan's clinical evaluation.

There is an extensive body of literature supporting femoropopliteal stenting including in 'real-world' registries  The principles of evaluating safety at 30 days and effectiveness (patency of the stented segment) at 12 months are well-established clinical endpoints for such a real-world registry. However, the specific attributes of the BioMimics 3D stent (promotion of swirling blood flow and improved biomechanical compatibility within the femoropopliteal artery) have the potential for chronic outcome benefits supporting the longer term follow-up objective of this study.

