#### 3.4 Study Duration and Follow-Up

It is anticipated that enrolment will commence in August 2016 and is expected to continue until August 2018. The last patient visit is expected in 2021.

Patient follow up will be in accordance with standard of care. Data will be collected according to the following schedule: baseline (medical history), index procedure through discharge, 30 days ( $\pm$  7 days), 12 months (365 days  $\pm$  60 days), 24 months (730 days  $\pm$  60 days) and 36 months (1095 days  $\pm$  60 days). Follow-up may be conducted by clinic visit or telephone, according to site standard of care.

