### 4.2 Secondary Outcome Measures

• Acute technical success defined as the achievement of a final residual diameter stenosis <30% at the end of the procedure

- Acute procedural success defined as both acute technical success and absence of the following adverse events: death, stroke, MI, acute onset of limb ischemia, index bypass graft or treated segment thrombosis, and/or need for urgent/emergent vascular surgery, within 72 h of the index procedure.
- Incidence of individual components of MAE (death, any major amputation performed on the index limb or CDTLR) at 30 days, 12, 24 and 36 months
- Overall rate and incidence of adverse events from Day 0 through completion of study follow-up at Month 36.
- Stent patency rate assessed by duplex ultrasound, as available, determined at Months 12, 24 and 36. This will be assessed using values of PSVR >2.0, >2.4; >2.5; and >3.5 each to indicate loss of patency on duplex ultrasound.
- Clinical outcome: comparison of Rutherford Clinical Category measured at Baseline, Day 30, Months 12 24 and 36.
- Functional outcome: comparison of the ankle brachial index (ABI) measurement at Baseline, within 30 days after index procedure, then at Months 12, 24 and 36.
- Incidence of reported stent fractures through 36 months.
- Operator assessment of device use

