### 5.2 Informed Consent

Written Consent for Data Collection with the Ethics Committee (EC)/Institutional Review Board (IRB) approved consent form will be obtained for all patients prior to Study procedure and collection of any Study-specific information. There are no additional procedures or tests required in addition to routine standard of care.

The patient shall be given adequate time to read the Written Consent for Data Collection consent form and have the data collection and data transmission procedures explained prior to signing the Informed Consent form. All patients providing informed consent for data collection are to receive copies of their signed informed consent documentation. The consent process may be obtained up to 30 days prior to enrolment in the Study.

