### 6.0 DATA COLLECTION PROCEDURES

### 6.1 Visit Schedule

Study participation will last for a total of 36 months ( $\pm$  60 days). Data collection will be completed at baseline index hospitalisation, 30 days ( $\pm$  7 days), 12 months (365 days  $\pm$  30 days), 24 months (730 days  $\pm$  60 days) and 36-months (1095 days  $\pm$  60 days). Follow-up may be by clinic visit or telephone according to site standard of care.

A summary schedule of the data collection for tests and evaluations is in Table 1. Data should only be collected if tests and evaluations are completed per standard of care.

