### Table 1: Data Collection Schedule

Assessment	Baseline	Day 0 Index Procedure (Enrolment / Treatment)	Follow-up Visits 30 days (± 7 days), 12 months (365 days ± 30 days), 24 months (730 days ± 60 days), 36-months (1095 days ± 60 days)
Informed Consent	Х	-	
Medical History	х		х
ABI/TBI	X		х
Rutherford Clinical Category (RCC)	Х		х
Procedural data & technical success		X**	
Index procedure angiographic assessments		х	
Follow-up standard of care imaging assessments, as applicable: • Angiography • Duplex ultrasound • X-ray			х
Concomitant antiplatelet and anticoagulant medications	х	х	Х
Adverse Event Assessment		х	х
Subsequent intervention (target limb)		×	х
Device use questionnaire (operator)		Х	
Walking Impairment Questionnaire (WIQ)*	0		0

\*WIQ is optional (O) and may be collected if standard of care at site.

\*\* Females of childbearing potential should have a negative pregnancy test before procedure (according to site standard of care)

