### 9.4 Secondary Endpoint Analysis

All secondary endpoints will be tabulated. Means, standard deviations and sample size will be used to summarise continuous characteristics. Distributions of continuous data will be examined and if nonnormality is exhibited, medians and interquartile ranges will be presented. Frequencies and percentages will be used to summarise categorical characteristics. Measures collected serially over time (for example, Rutherford Clinical Category) will be presented at each time point, and the measure at each time point will be compared to the baseline measure as well as tested for trends. All available data will be used for each endpoint and no imputations will be done. The mITT analysis set will be used for these analyses. As a secondary analysis, the PP analysis set will be displayed.

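### Duplex patency at 12, 24 and 36 months can be biased in either direction by who is scanned, and the plan neither measures nor limits this

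*Combined protocol and SAP*

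**What the plan says.** **Endpoint.** Section 4.2 lists "Stent patency rate assessed by duplex ultrasound, as available, determined at Months 12, 24 and 36", and adds: "This will be assessed using values of PSVR >2.0, >2.4; >2.5; and >3.5 each to indicate loss of patency on duplex ultrasound". Section 12 defines primary stent patency differently, as a composite that also requires freedom from CDTLR.

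**Where the scans come from.** Section 5.2: "There are no additional procedures or tests required in addition to routine standard of care". Section 6.1: "Data should only be collected if tests and evaluations are completed per standard of care". Section 3.4: "Follow-up may be conducted by clinic visit or telephone, according to site standard of care". Table 1 has the row "Follow-up standard of care imaging assessments, as applicable", with duplex as one of three modalities. Section 6.4 asks for imaging data with patency and fracture findings. Neither place lists the reason for the scan. Section 5.4 accepts that some observations will be missing because practice differs between sites.

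**Analysis.** Section 9.4: "All available data will be used for each endpoint and no imputations will be done". Section 9.7 plans no imputation and says nothing specific about unscanned patients. The between-site comparison in Section 9.5 covers the primary outcomes only. The site selection criteria in Section 10.3 do not ask whether duplex surveillance is routine.

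**The concern.** Suspected restenosis is an ordinary reason for a duplex scan. At a site that scans everyone, nearly all patients contribute to the patency rate. At a site that scans on symptoms, patients with suspected failure are more likely to contribute than well patients followed by telephone. Entry into the denominator then depends on the outcome, and a larger sample does not cure that.

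There is also a path the other way. Section 4.2 reads loss of patency from duplex alone. A patient who has had CDTLR and is not scanned again may simply be missing, although under Section 12 that patient is a failure.

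The stake is how the long-term results are read. Section 1.7 says of registries of this kind that safety at 30 days and "effectiveness (patency of the stented segment) at 12 months are well-established clinical endpoints", and it justifies the longer follow-up by possible chronic benefit. If routine surveillance thins out after Month 12, a change in patency by Month 36 could partly be a change in who is scanned. The report would not show how much.

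**Working it through.** **The plan's own figure.** There is none for patency: no assumed rate, scan completeness or precision. The nearest is Section 9.6, a width of about 8% for a 75% rate with 10% attrition. With n = 500 × 0.9 = 450, 2 × 1.96 × √(0.75 × 0.25 / 450) = 8.0%, so it is reproduced. It concerns CDTLR and says nothing about selection.

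**Inputs.** True 12-month patency of 80% is an assumption; Section 1.4 cites reported rates above 80%. All scan probabilities, symptom rates and CDTLR fractions below are also assumptions, because the documents give none.

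**1. Failed stents more likely to be scanned.** Let r be the scan probability for failed stents divided by that for patent ones. Observed patency = 0.8 / (0.8 + 0.2r).

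| r | Calculation | Observed patency |
|---|---|---|
| 1 | 0.8 / 1.0 | 80.0% |
| 1.5 | 0.8 / 1.1 | 72.7% |
| 2 | 0.8 / 1.2 | 66.7% |
| 3 | 0.8 / 1.4 | 57.1% |

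**2. How this depends on routine coverage.** Let a fraction c of patients be scanned routinely. Among the rest, only symptomatic patients are scanned, with probability 0.9. Let 10% of patent patients and 50% to 70% of failed patients be symptomatic. A symptomatic patient is scanned with probability c + 0.9(1 − c), an asymptomatic one with probability c.

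For c = 0.75 these are 0.975 and 0.75. Scanned and patent: 0.8 × (0.1 × 0.975 + 0.9 × 0.75) = 0.618. Scanned and failed, with 50% symptomatic: 0.2 × (0.5 × 0.975 + 0.5 × 0.75) = 0.1725. Observed patency: 0.618 / 0.7905 = 78.2%.

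| Routine coverage c | Observed patency | Error (points) |
|---|---|---|
| 100% | 80% | 0 |
| 75% | 77.3% to 78.2% | −2.7 to −1.8 |
| 50% | 72.8% to 75.0% | −7.2 to −5.0 |
| 25% | 63.7% to 68.4% | −16.3 to −11.6 |
| 0% | 36.4% to 44.4% | −43.6 to −35.6 |

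At 50% coverage about 261 to 270 of 450 patients are scanned. The Agresti-Coull 95% interval is then about 10.5 points wide, a half-width of about 5.3, so the bias is about as large as the sampling error.

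**3. The opposite direction.** If a fraction t of all patients has CDTLR, is not rescanned and is not counted as failed, and all others are scanned, observed patency = 0.8 / (1 − t):

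- t = 5%: 0.8 / 0.95 = 84.2%
- t = 10%: 0.8 / 0.90 = 88.9%
- t = 15%: 0.8 / 0.85 = 94.1%

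**4. Bounds without a selection model.** If a fraction f is scanned and 80% of those are patent, patency in all patients lies between 0.8f (every unscanned stent failed) and 0.8f + (1 − f) (every unscanned stent patent):

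- f = 90%: 72% to 82%
- f = 70%: 56% to 86%
- f = 50%: 40% to 90%

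**The case against.** The strongest defence is that this is an observational registry that mandates no tests. Patency is one of nine secondary measures, the study is declared descriptive and unpowered (Sections 9.0 and 9.6), and neither primary endpoint is a duplex measure. The limitation is visible in the endpoint's wording and in Section 5.4, and Section 9.0 reports N beside each percentage. CDTLR, amputation, Rutherford category, ABI and fractures also run to Month 36, so long-term benefit does not rest on duplex alone. All of this stands, and it limits the weight of the point. It explains why scanning is selective, but not why the reason for a scan and the number due are left out. N alone does not show how many patients should have been scanned.

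A reader might infer more than the documents support:

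- **That the rate shows who was scanned rather than how stents perform.** Too absolute. There is no bias with universal routine scanning, and only 2 to 3 points at 75% coverage under the assumptions above.
- **That symptom-driven scans are known to be pooled in.** This is a fair inference from standard-of-care collection, but no passage describes the mix of scans. Patency is tied to visit time points, and nothing says that every scan between visits enters the rate.
- **That the reason is recorded nowhere and scans could never be separated.** The eCRF is not in the documents; the item is only absent from the listed data. Rutherford category, ABI and target-limb events are partial proxies for symptoms, though no such use is planned.
- **That the bias runs against the stent.** The direction is not established, as step 3 shows.
- **That a main table of scheduled scans only would solve it.** It would drop failures found by a symptom-driven scan. If half the failures go that way, a true 80% reads as 0.8 / (0.8 + 0.1) = 88.9%.

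**Conclusion.** The point holds in a limited form. Followed as written, the plan can give a patency rate biased by outcome-dependent scanning. It collects nothing listed, and plans no analysis, that would show how large the bias is or which way it runs.

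The size is unknown. With true patency of 80%, the illustrations run from no error, through 2 to 3 points at 75% routine coverage, to an observed 57% if failed stents are three times as likely to be scanned, and lower still if almost no scanning is routine. In the other direction they reach 84% to 94% if patients with CDTLR drop out. These figures rest on assumed scan, symptom and CDTLR rates; only the 80% has an anchor in the documents.

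The primary safety and effectiveness endpoints are not duplex measures. The change should be made because it is cheap and because the reason for a scan is best captured when the scan is done; the study's primary conclusions do not depend on it.

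**What to change.** 1. **Data.** Add one eCRF field to each duplex: scheduled surveillance or symptom-driven. At site initiation, record whether the site's standard of care includes duplex at Months 12, 24 and 36.
2. **Section 9.4.** At each time point report number scanned over number due, with due defined. Show patency for sites with routine surveillance at that time point alongside patency from all available scans.
3. **Failures and unscanned patients.** In both tables, count a patient with earlier documented loss of patency on any scan, or with CDTLR, as not patent, in line with the Section 12 definition. Give best-case and worst-case bounds for patients due but not scanned. Counting known failures removes the upward path only; the routine-site table and the bounds address the downward one.

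The Month 12 window also needs reconciling, because it decides which scans count: Section 3.4 gives ±60 days, while Section 6.1, Table 1 and Section 6.4 give ±30.

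**Cost.** One extra field, one site-initiation question and SAP wording, with no added scan or visit. The routine-site table will have fewer patients and so a wider interval.

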**Limb Ischemia**: Deficient supply of oxygenated blood to the tissues in the limbs that is due to obstruction of the inflow of arterial blood characterised by pain and/or discoloration of the limb and/or tissue loss.

Luminal Patency: Restenosis <50% as determined by angiography or duplex ultrasound.

**Major Adverse Event (MAE):** An MAE comprises all-cause death, any major amputation performed on the target limb or clinically-driven target lesion revascularisation.

**Myocardial Infarction (MI)**: Evidence of myocardial necrosis in a clinical setting consistent with myocardial ischemia.

**Patency, Primary Stent:** Patency is defined as the composite of (1) freedom from more than 50% restenosis within the stented segment and (2) freedom from clinically-driven target lesion revascularisation (TLR).

**Patency, Tibioperoneal Run-Off:** Subject has at least one patent tibioperoneal run-off vessel with <50% stenosis confirmed by angiography.

Perforation: Puncture of an arterial wall.

**Pseudoaneurysm**: Disruption of the arterial wall characterised by an out-pouching or pocket with swirling, flowing blood outside of the confines of the arterial lumen.

Recurrent Occlusion: Occlusion (i.e. total obstruction of vessel lumen) after a successful canalisation.

**Recurrent Thrombosis**: Thrombosis (i.e. sub-total obstruction of vessel lumen) following successful treatment.

**Reference Vessel Diameter, Proximal (RVD**prox): Diameter of normal vessel immediately proximal to the treated segment.

Reference Vessel Diameter, Distal (RVDdist): Diameter of normal vessel immediately distal to the treated segment.

**Renal Failure (Acute):** Acute post-operative renal insufficiency resulting in one or more of the following: (a) increase of > 1.0 mg/dl in serum creatinine from most recent prior measured level, and current measured absolute value is > 2.0 mg/dl; (b) a new requirement for dialysis.

**Renal Insufficiency**: An increase in serum creatinine of  $\geq$  1.0 mg/dl over previous value requiring medical treatment but which does not require dialysis to resolve.

**Respiratory Failure:** New onset of respiratory insufficiency that requires placement of endotracheal tube and/or pneumothorax with or without chest tube.

**Respiratory Insufficiency:** Deterioration of subject's respiratory efforts that require supportive or medical treatment.

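### The plan neither defines the Month 24 and Month 36 patency denominator nor says that an earlier loss of patency is retained, so visit-only rates are permitted

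*Combined protocol and SAP*

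**What the plan says.** Section 4.2 defines the outcome as "Stent patency rate assessed by duplex ultrasound, as available, determined at Months 12, 24 and 36", with "PSVR >2.0, >2.4; >2.5; and >3.5 each to indicate loss of patency on duplex ultrasound". It gives no denominator and does not refer to the patency definition in Section 12.0.

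Scans are not mandated. Section 6.1 states that "Data should only be collected if tests and evaluations are completed per standard of care", and Section 3.4 that "Follow-up may be conducted by clinic visit or telephone, according to site standard of care". A telephone contact yields no scan.

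For the analysis, Section 9.4 says of repeated assessments that "Measures collected serially over time (for example, Rutherford Clinical Category) will be presented at each time point". Categorical outcomes are tabulated as counts with percentages. On missing values the same section says "All available data will be used for each endpoint and no imputations will be done". Section 9.7 repeats that nothing is imputed. Its known-status rule deals with status learned after a missed visit; it does not address a loss seen before one.

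Section 12.0 defines primary stent patency as a composite of "freedom from more than 50% restenosis within the stented segment" and freedom from clinically-driven target lesion revascularisation (CDTLR). Section 9.0 provides Kaplan-Meier plots for time-to-event data but does not name patency among them.

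**The concern.** Take a patient whose Month 12 duplex is above the threshold, who is not treated, and whose Month 24 follow-up is a telephone call. Under a visit-only calculation this patient is a failure at Month 12 and is in neither numerator nor denominator at Month 24. A missed scan has removed a known failure. Under a freedom-from definition, that patient has failed at every later time point.

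The opposite can also happen. Where scanning is prompted by symptoms, known failures are scanned more often than patent stents and the rate is too low. Table 1 and Section 6.4 list follow-up imaging but do not list the reason for a scan, so the two patterns may be hard to tell apart.

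The exposed group is mainly restenosis seen on duplex, left untreated and not rescanned. A patient who goes on to CDTLR would count as a failure under the Section 12.0 composite without a further scan, if that composite is the one used.

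At stake is the long-term patency curve. Section 1.7 justifies the extended follow-up by possible chronic benefit, and Sections 9.8 and 11.4 allow results to be presented, published and used in marketing. A rate that moves with rescanning habits would describe whoever was scanned, not the patients who received the stent.

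**Working it through.** The plan states no patency rate, scan rate or patency sample size, so there is no figure to reproduce. All rates below are assumptions.

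**Inputs.** 20% of stents lose patency by Month 12, and 10% of the remainder by Month 24. True Month 24 patency = 0.80 × 0.90 = 0.72. The new losses are 0.80 × 0.10 = 0.08 of the cohort.

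**Formula.** Visit-only patency = patent stents scanned ÷ all stents scanned at that visit. Losses not yet seen are scanned at the same rate as patent stents. Only known losses have a different rate.

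**A. Every stent scanned at Month 12 (all 0.20 are known losses)**

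| Month 24 scan rate: others / known losses | Calculation | Visit-only |
|---|---|---|
| 60% / 60% | 0.432 ÷ (0.432 + 0.048 + 0.120) | 72% |
| 60% / 30% | 0.432 ÷ (0.432 + 0.048 + 0.060) | 80% |
| 60% / 0% | 0.432 ÷ (0.432 + 0.048) | 90% |
| 40% / 80% (symptom-led) | 0.288 ÷ (0.288 + 0.032 + 0.160) | 60% |

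**B. Month 12 scanning also incomplete.** Month 12 scanning is at random, at the Month 24 rate for others. At 60%, known losses are 0.12 and unseen losses 0.08. At 40%, they are 0.08 and 0.12. The third term in each denominator is the unseen Month 12 losses scanned at Month 24.

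| Scan rate: others / known losses | Calculation | Visit-only |
|---|---|---|
| 60% / 30% | 0.432 ÷ (0.432 + 0.048 + 0.048 + 0.036) | 76.6% |
| 60% / 0% | 0.432 ÷ (0.432 + 0.048 + 0.048) | 81.8% |
| 40% / 80% | 0.288 ÷ (0.288 + 0.032 + 0.048 + 0.064) | 66.7% |

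**C. Through Month 36.** Assume 500 stents, losses of 20%, then 8%, then 6% of those still patent, a 70% scan rate, and no rescan of known losses.
- True patency: 400/500 = 80.0%, 368/500 = 73.6%, 345.9/500 = 69.2%.
- Visit-only, Month 12: 280 ÷ (280 + 70) = 80.0%.
- Visit-only, Month 24: 257.6 ÷ (257.6 + 43.4) = 85.6%. Here 43.4 = 0.70 × (32 new + 30 unseen).
- Visit-only, Month 36: 242.1 ÷ (242.1 + 28.5) = 89.5%. Here 28.5 = 0.70 × (22.1 new + 18.6 unseen).

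The reported rate rises while the true rate falls. If known losses were also rescanned at 70%, visit-only patency would equal the true 80.0 / 73.6 / 69.2%.

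**D. Candidate corrections, on the inputs of A**
- Adding all known losses to the patients scanned at Month 24: 0.432 ÷ (0.432 + 0.048 + 0.200) = 63.5% for both 60% rows with differing rates, and 0.288 ÷ (0.288 + 0.032 + 0.200) = 55.4% for the symptom-led row. Both are well below 72%.
- Time to first loss, with censoring at the last patent scan: 0.80 × (1 − 0.048/0.480) = 72%, or 0.80 × (1 − 0.032/0.320) = 72%. It recovers the true value in every row of A.

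**E. Why missed visits need interval censoring.** Take B at 60% and treat the detecting scan as the date of loss.
- The Month 12 risk set is 0.60 + 0.40 × 0.60 = 0.84 with 0.12 losses, so Kaplan-Meier gives 1 − 0.12/0.84 = 85.7% instead of 80%.
- At Month 24 the risk set is 0.48 × 0.60 + 0.24 = 0.528, with 0.0288 + 0.24 × 0.28 = 0.096 losses. This gives 0.857 × (1 − 0.096/0.528) = 70.1%.

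An interval-censored fit places a loss first seen at Month 24, with no Month 12 scan, anywhere in 0 to 24 months. On these inputs it returns 80% and 72%.

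**The case against.** The strongest reply is that the plan never says patency is calculated only among those scanned at each visit. A reader might infer that it does, but the documents only leave the denominator open. The rule to use all available data could include earlier scans, the Kaplan-Meier sentence could cover patency, and the Section 12.0 definition is cumulative. That stands against a claim of fact. It does not settle the matter, because none of these passages names the Section 4.2 patency rate or says that an earlier loss is kept, while the fixed-visit wording and visit-by-visit percentages point the other way.

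A reader might also infer that patency will appear to rise. The documents do not support this: the direction depends on rescan rates that they do not give, and equal rescanning produces no distortion. Nor should the 60% to 90% range be taken as the expected size, since it needs complete scanning at Month 12, which sits badly with scans taken as available.

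It would be tempting to say that the reason for each scan is not recorded. The case report form is not among the documents, so that cannot be known. Rutherford category, ABI, target-limb vascular events and subsequent interventions are also collected and would help interpretation.

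Finally, the study is descriptive, the wording of Section 4.2 discloses that scans are incomplete, and CDTLR is also reported at Months 24 and 36, so patency is not the only long-term evidence. These points limit the importance of the gap but do not close it.

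**Conclusion.** The point holds as a gap in the analysis rules. The plan does not define the Month 24 and Month 36 patency denominator and does not retain an earlier loss. Read as written, it leads most naturally to visit-only patency, which can move up or down with site rescanning habits and does not match the Section 12.0 definition.

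On assumed rates with a true value of 72%, visit-only patency is about 67% to 82% when Month 12 scanning is also incomplete, and 60% to 90% when it is complete. These figures treat all losses as exposed. If CDTLR counts as a loss without a rescan, only untreated, unrescanned restenosis is affected, and the documents do not size that group. The primary safety and effectiveness endpoints do not depend on this rule. The change should be made, but the study's main results do not turn on it.

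**What to change.** In Sections 4.2 and 9.4:

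- Define patency, for each PSVR threshold, as time to first loss: the first duplex above the threshold, scheduled or unscheduled, or CDTLR. State that a loss is not reversible.
- Estimate it at Months 12, 24 and 36 by Kaplan-Meier, censoring at the last patent scan, or by an interval-censored method where visits are missed. State how a CDTLR after the last scan is entered, since CDTLR can be ascertained without a study duplex and continued patency cannot.
- Do not simply add known failures to each visit's scanned patients; that biases patency downward when scanning is incomplete.
- Report number scanned over number eligible at each visit.
- Record whether each duplex was routine or for symptoms, if this is not already captured, and add a sensitivity analysis on routine scans alone. Time to first loss does not by itself remove bias when new losses are more likely to be scanned because they cause symptoms.

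No extra scans are needed. The cost is a revised analysis rule, possibly one data field, and one extra table. Later patency may look less favourable than visit-only rates, and the routine-only analysis will rest on fewer patients.

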### 6.4 Follow-Up

The following data will be collected at **Day 30** ( $\pm$  7 days), **Month 12** (365 days  $\pm$  30 days), **Month 24** (730 days  $\pm$  60 days) and **Month 36** (1095 days  $\pm$  60 days) post Index Procedure:

- Relevant medical history including peripheral interventions (target limb)
- Physical examination (as available)
  - Ankle Brachial Index (ABI, or TBI, if applicable)
  - Rutherford Clinical Category
- Concomitant antiplatelet and anticoagulant medication
- Imaging data including patency assessment, evidence of stent fracture
- Adverse events

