**Restenosis:** Reoccurrence of narrowing or blockage or target lesion. Recurrence of  $\geq$  50% diameter stenosis within ± 5 mm proximal and/or distal to the target lesion as measured by duplex ultrasound or angiography

**Retroperitoneal Bleed:** Bleeding into the back of the abdomen from a vascular access or puncture site.

**Rutherford Clinical Category Scale:** Clinical scale identifying three grades of claudication and three grades of critical limb ischemia ranging from rest pain alone to minor and major tissue loss .

Category	Clinical Description
0	Asymptomatic
1	Mild claudication
2	Moderate claudication
3	Severe claudication
4	Ischemic rest pain
5	Minor tissue loss
6	Ulceration or gangrene

**Stent Fracture:** Defined as clear interruption of stent strut observed in a minimum of two projections, determined by core lab examination of X-ray images.

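### Section 4.2 measures stent patency by duplex alone, Section 12 also uses angiography and clinically-driven TLR, and the plan does not say which governs; under 4.2 as written, some known failures leave the rate

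*Combined protocol and SAP*

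**What the plan says.** **Endpoint.** Section 4.2, like the synopsis, lists "Stent patency rate assessed by duplex ultrasound, as available, determined at Months 12, 24 and 36". Four PSVR cut-offs (2.0, 2.4, 2.5 and 3.5) are named, "each to indicate loss of patency on duplex ultrasound". There is no angiographic criterion and no mention of revascularisation.

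**Data collected.** Table 1 lists "Follow-up standard of care imaging assessments, as applicable: • Angiography • Duplex ultrasound • X-ray". Section 6.4 asks for "Imaging data including patency assessment, evidence of stent fracture" without naming a modality. No follow-up imaging is mandatory. Section 6.1 states: "Data should only be collected if tests and evaluations are completed per standard of care".

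**Definitions.** Section 12 has three relevant entries:
- "Luminal Patency: Restenosis <50% as determined by angiography or duplex ultrasound".
- Restenosis is a recurrence of at least 50% within 5 mm of the target lesion, "as measured by duplex ultrasound or angiography".
- Primary stent patency is a composite of no restenosis above 50% in the stented segment and no clinically-driven TLR. No modality is named.

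**Analysis.** Section 9.4 uses whatever data are available for each secondary endpoint and imputes nothing. Section 9.7 treats a status ascertained out of window as known, but does not address a status shown by a different imaging method.

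**The concern.** Sections 4.2 and 12 describe different endpoints under similar names, with no cross-reference. One is a duplex velocity reading. The other is a composite that includes clinically-driven TLR and, through the restenosis definition, can be read from an angiogram.

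The difference matters for a stent with no duplex at the time point that was shown restenosed or occluded on a follow-up angiogram, or that was retreated. Under 4.2 there is no PSVR and so no patency status. With no imputation, the stent is dropped although its failure is in the database. Under Section 12 it is a failure.

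If angiograms are ordered mainly when failure is suspected, the dropped stents are mostly failures and the reported rate is too high. Section 1.7 describes effectiveness at 12 months in terms of patency of the stented segment, so readers are likely to give this figure weight although it is a secondary measure.

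**Working it through.** **No figure to reproduce.** The plan gives no patency rate, duplex completion rate or patency precision. The interval widths in Section 9.6 concern MAE and CDTLR and do not bear on this point.

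**How each text classifies a stent with no duplex**

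| Stent | 4.2 as written | Section 12 primary stent patency, read with its restenosis entry |
|---|---|---|
| Restenosis or occlusion on angiogram, no CDTLR | No status; leaves the rate | Loss of patency |
| CDTLR performed | No status; leaves the rate | Loss of patency |
| Angiogram without restenosis | No status; leaves the rate | No restenosis shown; patent if also free of CDTLR |

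The first row is not covered elsewhere. CDTLR in Section 12 requires a revascularisation, recurrent symptoms, an angiographic stenosis of at least 50% and new distal ischemic signs. An angiographic failure managed conservatively, or retreated without meeting all of these, is also absent from the primary effectiveness endpoint.

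**Size under assumed rates.** The 450 is 500 × 0.90, using the 10% attrition in Section 9.6. Every other input is an assumption: duplex in 60% (270 stents), of which 80% are patent (216). If *k* further stents are known failures without duplex, the rate becomes 216/(270 + *k*):

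- *k* = 5: 216/275 = 78.5%
- *k* = 9: 216/279 = 77.4%
- *k* = 14: 216/284 = 76.1%
- *k* = 22: 216/292 = 74.0%

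These values of *k* are about 1% to 5% of 450.

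**Range.** With duplex share *d*, duplex patency *p* and uncounted failures as share *a* of all patients, the overstatement is *p* × *a*/(*d* + *a*). Over *d* = 50% to 90%, *p* = 75% to 85% and *a* = 2% to 10%:

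- smallest: 0.75 × 0.02/0.92 = 1.6 points
- largest: 0.85 × 0.10/0.60 = 14.2 points

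**If CDTLR is counted as failure.** Take *d* = 70% (315 stents), *p* = 80% (252 patent) and *a* = 5% (22.5 stents). Counting all failures gives 252/337.5 = 74.7%, an overstatement of 5.3 points. If a fraction *f* of the 22.5 had CDTLR and are counted through it, the reported rate is 252/(315 + 22.5*f*):

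- *f* = 0.5: 77.2%, 2.6 points too high
- *f* = 0.8: 75.7%, 1.0 point too high
- *f* = 1: 74.7%, no excess

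If Section 12 applies in full, including angiographic restenosis, the excess is zero for any *f*.

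**If patent angiograms are also counted.** In the first illustration, adding 14 failures and 14 patent angiogram-only stents gives 230/298 = 77.2%, against 76.1% with the failures alone. The rate stays at 80% only with four patent for each failed, for example (216 + 56)/(270 + 70) = 272/340. The upward bias therefore depends on angiogram-only stents having worse patency than those with duplex.

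**The case against.** The strongest reply is that Section 12 already resolves this. Its primary stent patency entry has no modality limit, counts clinically-driven TLR as failure and, read with the restenosis entry, takes angiographic evidence. On that reading no failure is lost. This is a sound reading, and it limits the point: the loss is not certain, and a reader who infers that every stent failing on angiogram leaves the rate goes further than the documents do. It does not close the point, because 4.2 uses a different name, different criteria and no reference to Section 12.

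The affected group is also narrower than it first appears. Many treated, symptomatic failures will be CDTLR and are reported in the primary effectiveness endpoint and in CDTLR incidence at 12, 24 and 36 months. A reader might take bypass to be outside CDTLR, but the definition names no method of revascularisation and does not exclude surgery.

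Two further inferences are tempting and unsupported. One is that duplex overrides a contradictory angiogram; no rule for conflicting tests is stated in either direction. The other is that follow-up angiograms are known to be symptom-driven; the plan says only that imaging follows site standard of care, so this remains a plausible assumption.

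Finally, this is a descriptive secondary measure, openly labelled as duplex-based and as available. A duplex-only rate would be accurately described, which limits the weight of the point. It does not settle how stents already known to have failed are counted.

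**Conclusion.** The point holds as an unreconciled conflict between Sections 4.2 and 12. Under 4.2 as written, combined with 9.4, a stent whose failure is shown only on a collected angiogram, or that had CDTLR without a duplex, has no patency status and is not counted. If Section 12 governs in full, it is counted as a failure. The plan does not say which applies.

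The bias under 4.2 is probably upward, provided follow-up angiograms are mainly prompted by suspected failure. Its size cannot be established from the documents. The assumed rates above give falls of about 1.5 to 6.0 points from 80.0% in the first illustration and 1.6 to 14.2 points over the wider range; neither is an estimate for this study. The effect shrinks if most such stents reach CDTLR and that is counted. The primary endpoints are unaffected. The change is worth making because it is cheap and patency will be read as a main result.

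**What to change.** In 4.2 and 9.4, state that the endpoint follows Section 12 and specify:

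- **Loss of patency at a time point:** a prior CDTLR, or restenosis or occlusion on duplex (at each PSVR cut-off) or on a follow-up angiogram up to that time point, including unscheduled angiograms.
- **Patent on angiogram:** an in-window angiogram without restenosis counts as patent in a stent with no earlier loss. Section 3.4 gives ±60 days for Month 12, while 6.1, Table 1 and 6.4 give ±30 days; these must be reconciled first.
- **One limit and one segment:** Section 12 has below 50% as patent, above 50% as failure, and at least 50% within 5 mm of the lesion as restenosis. A stenosis of exactly 50% is therefore treated inconsistently, and the segment differs between entries.
- **Four PSVR analyses:** apply the angiographic result and prior CDTLR identically in each, since an angiogram has no PSVR.
- **Conflicting tests:** prespecify a rule.
- **Reporting:** give the duplex-only rate beside the combined rate, with the numbers having duplex, angiogram only and neither at each time point.

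The cost is protocol and SAP wording and some programming; no new data are needed. The downside is that if angiograms are mostly symptom-driven, the combined rate may be somewhat pessimistic, the more so because earlier failures carry forward while patent stents need an in-window image. Both rates should therefore be shown.
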